2.1.2 Secondary Objectives

1. To compare the proportions of local and systemic reactions (other than moderate/severe injection site pain) after aIIV3 and IIV3-HD in the full study population and by age-group (65-79 years and ≥ 80 years)
2. To describe and compare changes in health-related quality of life after aIIV3 and IIV3-HD in the full study population and by age-group
3. To compare serum hemagglutination inhibition (HAI) antibody titers after aIIV3 and IIV3-HD for each of the three influenza vaccine strains contained in the respective vaccine for that season in the full study population and by age (except for seroconversion for the H3N2 strain in the full study population)

2.1.3 Exploratory Objectives:

1. To describe how the reactogenicity events affect health-related quality of life after IIV3 and IIV3-HD in the full study population and by age-group
2. To describe and compare participant perceptions about the vaccination experience
3. To describe participant perceptions of methods of adverse event monitoring in older adults receiving influenza vaccines.
4. To describe injection site pain immediately after vaccination after aIIV3 and IIV3-HD
5. To describe and compare the proportions of immediate adverse events and unsolicited adverse events after aIIV3 and IIV3-HD in the full study population and by age-group (65-79 years and ≥ 80 years)
6. To describe factors (e.g., statin use) associated with reactogenicity to aIIV3 and IIV3-HD
7. To describe the safety of aIIV3 and IIV3-HD after repeat administration of the same product over 2 consecutive influenza seasons in a subset of subjects
8. To describe the relationship between reactogenicity and immunogenicity for aIIV3 and IIV3-HD
9. To explore factors (e.g., statin use) associated with immunogenicity for aIIV3 and IIV3-HD
10. To describe the immunogenicity of aIIV3 and IIV3-HD after repeat administration of the same product over 2 consecutive influenza seasons in a subset of subjects
11. To assess changes in serum hemagglutination inhibition at 1 month after aIIV3 and IIV3-HD vaccination, and at 6 months after vaccination in a subset of subjects

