4.2 Subject Exclusion Criteria

Subjects who meet any of the following criteria will not be eligible to participate in this study:

1. Influenza vaccine receipt during the current influenza season prior to study enrollment
2. Enrolled in this study during the 2017-18 (Year 1) influenza season
Note: Year 1 study participant will only be enrolled in Year 2 if they are participating in the sub-study on repeat vaccination
3. Has immunosuppression as a result of an underlying illness or treatment, or use of anti-cancer chemotherapy or radiation therapy within the preceding 12 months.
4. Has an active neoplastic disease (excluding non-melanoma skin cancer or prostate cancer that is stable in the absence of therapy) or a history of any hematologic malignancy*
**Participants with a history of malignancy may be included if, after previous treatment by surgical excision, chemotherapy or radiation therapy, the participant has been observed for a period that in the investigator's estimation provides a reasonable assurance of sustained cure*
5. Thrombocytopenia, bleeding disorder, or anticoagulant use contraindicating intramuscular injection
6. Receipt of blood or blood-derived products in the past three months
7. History of febrile illness ($\geq 100.0^{\circ}\text{F}$ or 37.8°C) within the past 24 hours prior to IIV administration (temporary deferral)
8. Contraindication to IIV receipt including history of severe allergic reaction after a previous dose of any influenza vaccine; or to a vaccine component*, including egg protein; or a latex allergy
**Formaldehyde, Octylphenol ethoxylate, neomycin, kanamycin, barium, cetyltrimethylammonium bromide (CTAB)*
9. Any history of Guillain-Barré syndrome

10. Mild to severe dementia as determined by the Mini-Cog tool and the Rowland Universal Dementia Assessment Scale (RUDAS)
11. Substance use that could interfere with study compliance
12. Receipt of any inactivated licensed vaccine within 2 weeks, or live attenuated licensed vaccine within 4 weeks prior to enrollment in this study, or planning receipt of any vaccines during the 42 days post-vaccination period (including pneumococcal vaccines)
13. Receipt of Shingrix (Zoster Vaccine Recombinant, Adjuvanted) or HEPLISAV-B (Hepatitis B Vaccine (Recombinant), Adjuvanted) vaccine within 6 weeks prior to enrollment in this study, or planning receipt of Shingrix or HEPLISAV-B during the 42 days post-vaccination period.

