4.3 Recruitment

Participants ≥ 65 years of age will be recruited from several sources at Duke University Medical Center (DUMC), Boston Medical Center (BMC), and Cincinnati using varying techniques. Study investigators will enroll at least 440 persons including at least 20% adults ≥ 80 years of age at Duke over two seasons (~220 participants per season), ~340 persons including at least 20% adults ≥ 80 years of age at Boston over two seasons (~170 per season), and ~100 persons including at least 20% adults ≥ 80 years of age at Cincinnati in 2018-2019 only. During 2017-2018 at Duke only, a subset of approximately 100 subjects will be assigned to receive an additional blood draw at day 181 (Section 5.2.1).

The general techniques for how subjects will be recruited include the following: Study staff, including PIs and study nurses, will approach their patients in clinic directly about the study during clinic visits; notify other health care professionals in their health system about the study via letters and flyers for potential referrals; notify potential subjects about the study via study registries and recruitment service programs; letters and talks to senior groups in various venues including Senior Centers and Continuing Care Retirement Communities; advertising in newspapers; flyers posted at senior locations; letters and talks to potential referral sources; and letter campaigns to older adults in the surrounding catchment area. More specific mechanisms to DUMC, BMC, and Cincinnati are described below.

At DUMC potential subjects will be approached via the following mechanisms: 1) Older participants of previous vaccine studies who have agreed to enroll in future studies; 2) Duke Center for Aging Human Subjects Registry, a unique long-standing registry of over 3000 individuals who volunteer for human studies; 3) Croasdaile and The Forest at Duke continuing care retirement communities. Medical care for these communities is provided by the Duke Division of Geriatrics, overseen by [name]; 4) Duke's "Aging" network of senior centers; senior activities; and referrals from professionals who work with seniors cultivated via the work

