A subset of approximately 60 subjects enrolled and vaccinated in the first year of the study at Duke will be included in a repeat vaccination sub-study in the second year of the study. The sub-study will explore the safety and immunogenicity of repeat vaccination with the same vaccine product in the subsequent influenza season. The study enrollment procedures will be the same, with the following modifications: At the time of enrollment in the first year, the subjects will be asked in sequential order if they would like to participate in a repeat vaccination sub-study during the next season. The first subjects enrolled at Duke (up to n=60), who express interest in this repeat vaccination sub-study will be included. Subjects need not consent to this part of the study to participate in the main study. In the first year, this convenience sample of sub-study subjects will undergo the same randomization procedures as other subjects in section 5.2.1. The subjects will complete procedures for the first study influenza season as in section 5.1. Contact information will be maintained, and subjects will be contacted and reminded to return to the study center in September/October the next influenza season. Upon return for the second year of the study, subjects will be consented for the sub-study and screened to see if they continue to meet the study eligibility criteria. In year 2, these subjects will receive the same vaccine product as in year 1, using the formulation licensed by FDA for the year 2 season; influenza strains included in the vaccines may be different in the consecutive years. These subjects will remain blinded to the vaccine product in Year 2. Year 1 study participants will only be enrolled in Year 2 of the study if they consent to and are still eligible for participating in the sub-study on repeat vaccination.

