6 LABORATORY ANALYSES

6.1 Influenza Hemagglutination Inhibition (HAI) Assay

Influenza Hemagglutination Inhibition (HAI) Assays will be performed on sera collected, contingent on additional funding. Briefly, reference wild-type, reassortant, or vaccine virus strains representative of the specific viral antigens included in the 2017-2018 and 2018-2019 influenza vaccine will be used to evaluate the relative levels of all three influenza strain-specific antibodies in participant serum samples collected pre- and 28 days post-vaccination from all study participants and at 181 days post-vaccination in a subset of 100 participants at Duke. To accomplish these activities all participant samples will be interrogated for influenza antibodies against the strains of interest using the influenza hemagglutination inhibition assay (HI). This assay is considered the “gold-standard” measure by which to evaluate seroconversion/seroprotection in response to seasonal influenza vaccination. This assay will be performed in accordance with the Duke Regional Biocontainment Laboratory Virology Unit's fully optimized and approved SOP (RVUSOP004 Influenza HI of Serum Samples). Briefly, test samples will be assayed by HAI as duplicate 2-fold dilution series starting at 1:10. Serum dilutions are then incubated with a concentration of virus verified to possess a known potential for red blood cell (RBC) agglutination. The presence of virus-specific antibodies is visualized via incubation of the virus-serum mixture with a RBC solution; the endpoint titer for a given dilution series is then expressed as the reciprocal of the final dilution in which complete HAI is observed. By convention, seronegative samples are defined as having an endpoint HAI titer < 40 and seropositive samples as having an endpoint titer of $\geq 1:40$; and seroconversion as a 4-fold change in endpoint titer relative to pre-immunization baseline or a change from <10 to $\geq 1:40$ ³⁷.

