7.1.2 Analysis Populations

Full Analysis Population:

- For Primary Objective 1 and Secondary Objective 1, the primary analysis population will be the Full Analysis Population; defined as all subjects who are randomized, vaccinated, and provide at least one day of complete data on the symptom diary.
- For Primary Objective 2 and Secondary Objective 2, the primary analysis population will be the Full Analysis Population; defined as all subjects who are randomized and vaccinated.

Immunogenicity Population:

For Primary Objective 3 and Secondary Objective 3 the primary analysis will be for the Immunogenicity Population; defined as subjects who received vaccine, provide baseline and Visit 4 blood draws of acceptable volume and quality within the protocol-defined time frame with

no protocol violations affecting immunogenicity. Protocol violations affecting the immunogenicity analyses will be defined in the Statistical Analysis Plan (SAP).

The Full Analysis Population is the primary population for analysis unless otherwise stated.

7.1.3 Primary Objective 1

- To compare the proportions of moderate/severe injection site pain after aIIV3 and IIV3-HD in the full study population
 - Hypothesis: the proportion of subjects who have moderate/severe injection site pain within the first week post-vaccination will be non-inferior for aIIV3 compared to IIV3-HD in the full study population

This objective will be assessed using a one-sided non-inferiority test with the alpha level set at 0.025 and non-inferiority margin of 5%.

The null hypothesis is aIIV3 is inferior to IIV3-HD in regards to the proportion of subjects having moderate or severe injection site pain in the first week post vaccination.

$$H_0: aIIV3 - IIV3-HD \geq 0.05 \text{ (5\%)}$$

The alternative hypothesis is aIIV3 is non-inferior to IIV3-HD in regards to the proportion of subjects having moderate or severe injection site pain in the first week post vaccination.

$$H_a: aIIV3 - IIV3-HD < 0.05 \text{ (5\%)}$$

The upper bound of the one-sided binomial confidence interval of the difference will be used to make this assessment.

7.1.4 Primary Objective 2

- To compare serious adverse events and events of clinical interest after aIIV3 and IIV3-HD in the full study population and by age-group

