To compare serum hemagglutination inhibition (HAI) antibody titers after aIIV3 and IIV3-HD for each of the three influenza vaccine strains contained in the respective vaccine for that season in the full study population and by age-group (except for seroconversion for the H3N2 strain in the full study population)

Responses to each influenza antigen will be analyzed, with the exception of seroconversion for H3N2, which is analyzed in Primary Objective 1. The proportion of subjects with seroprotection (pre- and post-immunization) seroconversion (4-fold rise from baseline) in the two treatment groups will be presented along with 95% exact binomial confidence intervals. A 95% confidence interval of the difference in proportions between the treatment groups will also be presented.

The GMTs for each influenza antigen, including H3N2, and 95% confidence boundaries will be presented for both treatment groups. A 95% confidence interval of the difference in GMTs between the treatment groups will also be presented. This information will also be prepared for the subset (N≥176) of subjects 80 or older.

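### The GMT comparison in section 7.1.8 leaves out the Day 1 titer; a Day 29 GMT ratio adjusted for it would probably be more precise at almost no cost

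*Combined protocol and SAP*

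**What the plan says.** Section 7.1.8 gives two statements on GMTs in the full immunogenicity set. The first is descriptive: "The GMTs for each influenza antigen, including H3N2, and 95% confidence boundaries will be presented for both treatment groups". The second is the only between-arm inference: "A 95% confidence interval of the difference in GMTs between the treatment groups will also be presented". The same output is promised for subjects aged 80 or older. The GMT item in section 2.2.2 names no study day, and neither section names a covariate, a regression model or a log scale.

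The analysis set for this objective is the Immunogenicity Population. Section 7.1.2 requires its members to "provide baseline and Visit 4 blood draws of acceptable volume and quality within the protocol-defined time frame". Section 6.1 says sera are run as a "duplicate 2-fold dilution series starting at 1:10", so titers lie on a log2 grid with a floor. Day 1 titer enters the planned analyses only through the seroconversion definition and the pre-immunization seroprotection proportion.

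Section 5.2.1 stratifies randomization by site and uses a separate block for those aged 80 or older. Section 2.1.2 frames the comparison by strain as "contained in the respective vaccine for that season in the full study population and by age". Section 7 describes itself as a summary and announces a fuller SAP, which is not among the documents. HAI testing depends on funding (sections 3.2.1 and 6.1).

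**The concern.** Everyone in the analysis set has a pre-vaccination sample, yet the planned GMT contrast makes no use of it. If subjects who start with high titers tend to end with high titers, part of the Day 29 spread is predictable from Day 1. Adjustment removes that part from the standard error.

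What is at stake is precision, not validity: randomization keeps the unadjusted contrast unbiased. Precision matters most where numbers are smallest. That means the group aged 80 or older (at least 176 subjects, 88 per arm) and any season-specific estimates, if the season wording means that the two years are reported separately.

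A smaller point needs clarification only. A *difference in GMTs* may be shorthand for a difference of log means, or it may mean an arithmetic difference. The same 1.5-fold effect is a difference of 20 at 60 versus 40 but 200 at 600 versus 400. A ratio reads alike across strains and seasons.

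**Working it through.** **Size of the analysis set.** Section 7.1.1 gives 390 per arm for H3N2 seroconversion (50% in both arms, 10-point margin, one-sided 0.025, about 80% power). The usual formula gives (1.960 + 0.842)² × 2 × 0.25 / 0.10² ≈ 393 per arm, and power at 390 is 79.8%, so the figure reproduces. The documents give no precision target or SD for GMTs.

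**Other group sizes, before drop-out.**
- Aged 80 or older: 176/2 = 88 per arm.
- Year 1 (section 4.3): 220 + 170 = 390, or 195 per arm.
- Year 2: 220 + 170 + 100 = 490, or 245 per arm.

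**Assumptions.** The within-arm correlation ρ between Day 1 and Day 29 log titers, the log2 SD and the share of baselines below 1:10 are not in the documents. Ranges are used for all three.

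**Analytic result without censoring.** The unadjusted standard error on the log2 scale is SD × √(2/n). Adjusting for Day 1 titer multiplies it by √(1 − ρ²), apart from one degree of freedom. For ρ = 0, 0.2, 0.3, 0.5 and 0.7 the factor is 1, 0.980, 0.954, 0.866 and 0.714, so the interval is 0%, 2%, 5%, 13% and 29% narrower. At ρ = 0.5 this equals 1/(1 − 0.25) = 1.33 times the subjects. With the degree of freedom counted, adjustment loses only when |ρ| is below about 0.04 (390 per arm) or 0.08 (88 per arm). The worst loss is about 0.1% and 0.3% of width.

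**Simulation on the assay scale.** There were 1,000 trials per cell. Latent log2 titers were bivariate normal with SD 1.8, Day 29 GMT was 80 in both arms, and there was no season effect. Titers were floored to two-fold steps from 10, and values below 10 were set to 5. Mean reduction in standard error:

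| Per arm | Baselines below 1:10 | ρ = 0 | 0.2 | 0.3 | 0.5 | 0.7 |
|---|---|---|---|---|---|---|
| 390 | 10% | −0.1% | 1.8% | 4.2% | 12.4% | 26.4% |
| 390 | 50% | −0.1% | 1.4% | 3.4% | 10.1% | 21.2% |
| 390 | 70% | −0.1% | 1.2% | 2.7% | 7.9% | 16.2% |
| 88 | 50% | −0.3% | 1.3% | 3.3% | 10.0% | 21.0% |

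**Example intervals.** True ratio 1.50, SD 1.5 log2 units, no censoring: 1.50 ×/÷ 2^(1.96 × 1.5 × √(2/n) × √(1 − ρ²)).

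| Per arm | Unadjusted | Adjusted, ρ = 0.5 |
|---|---|---|
| 390 | 1.30–1.74 | 1.32–1.70 |
| 195 (Year 1) | 1.22–1.84 | 1.25–1.79 |
| 88 (aged 80 or older) | 1.10–2.04 | 1.15–1.96 |

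**Season term, only if seasons are pooled.** The width factor is SD/√(SD² + p(1 − p)D²), with p = 390/880 and D the log2 shift in Day 29 GMT between seasons. At SD 1.5 and assumed shifts of 1-, 1.5-, 2- and 4-fold, the interval is 0%, 2%, 5% and 17% narrower.

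**Scale.** At SD 1.5 and 390 per arm, GMTs of 60 and 40 have intervals 54.1–66.5 and 36.1–44.3. Combining their log half-widths in quadrature returns the ratio interval 1.30–1.74. The unadjusted ratio is therefore recoverable from output already promised; the adjusted one is not.

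**The case against.** The strongest reply is that nothing is broken. The unadjusted estimate is unbiased, section 7.1.8 sets no margin or test for GMTs, and at 390 per arm a move from 1.30–1.74 to 1.32–1.70 changes no reading. Section 7 is a summary, and covariates are ordinary SAP content. The gain rests on a correlation that no document supplies, and at 0.3 or below it is 5% or less. Seroconversion already uses the baseline.

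Much of this stands: it is a missed efficiency, not an error, and the gain may be small. It does not remove the point. Section 7.1.8 states a specific contrast and does not defer it, whereas section 7.1.10 and the immunogenicity protocol-violation definitions are expressly deferred. A SAP that follows the text would omit the baseline. Seroconversion uses Day 1 titer in a dichotomy and does nothing for the GMT interval.

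Three narrower objections also deserve an answer.
- The 195 and 88 per arm are enrolment targets, while 390 is an evaluable number. With the same allowance for loss, 88 × 780/880 = 78 per arm, and the example becomes 1.08–2.08 unadjusted against 1.13–1.99 at ρ = 0.5. The percentage gain is unchanged.
- The season figures lapse if results are reported by season.
- An adjusted ratio will not equal the ratio of the displayed unadjusted GMTs, so the table must say so.

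**Conclusion.** The concern holds. The only between-arm GMT contrast in the plan does not specify use of the Day 1 titer, although every analysed subject must have provided a Day 1 sample. Adjustment narrows the log-scale interval by 0% to 29% for assumed correlations from 0 to 0.7 without censoring, and by about 0% to 21% if half the baselines are below 1:10. The loss if there is no correlation is about 0.1% to 0.3% of width. That imbalance makes the change worth making.

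Confidence in the size of the gain is only moderate, because correlation, SD and censoring are all assumed. The result is secondary and estimation-only and depends on HAI funding. No stated sample size, power figure or primary conclusion is affected. The log-scale question is a clarification, not a second fault.

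**What to change.** Replace the sentence on the GMT contrast in section 7.1.8 with wording such as:

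> For each antigen, the Day 29 GMT ratio (aIIV3/IIV3-HD) with its 95% CI will be estimated from a linear model of log2 Day 29 titer on vaccine group, log2 Day 1 titer, season, site and age group, and also shown by season. Titers below 1:10 will be assigned one pre-stated value. Each subject contributes one record; Year 2 records of repeat vaccinees are excluded.

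Drop the age-group term within 65–79 and within 80 or older, and drop the season term in season-specific output, where Cincinnati appears only in Year 2. Site and age group are included because randomization uses them. No interaction terms are needed. Keep the unadjusted per-arm GMTs with their intervals, and footnote that the adjusted ratio need not equal their ratio.

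The one-record rule is needed because section 4.2 lets Year 1 subjects re-enter for the sub-study ("Year 1 study participant will only be enrolled in Year 2 if they are participating in the sub-study on repeat vaccination") and, under section 4.3, "In year 2, these subjects will receive the same vaccine product as in year 1". Their second-year titers are repeat measurements, not new randomized subjects.

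A simple fold-rise comparison is not an equivalent fix. With equal SDs its variance factor is 2(1 − ρ), which is worse than no adjustment when ρ is below 0.5.

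The cost is wording only. No sample, visit or assay is needed beyond the Day 1 and Day 29 titers already planned.

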7.1.9 Sensitivity Analyses

For Primary Objective 1 a sensitivity analysis will be performed on the following sub-group of the Full Analysis Population: subjects who provided complete/informative symptom diary information for injection-site pain (i.e., eight days of completed pain field data on diary or graded pain if present) and have no specified protocol violations as described in the Manual of Operations. This a supporting safety analysis.

7.1.10 Exploratory Objectives

The analysis for the exploratory objectives will be detailed in the comprehensive Statistical Analysis Plan.

7.2 Data Management

The novel Vanderbilt-designed resource developed specifically for online collection of research information, the Research Electronic Data Capture (REDCap) platform (<https://projectredcap.org/>), will be used to design study forms, including the reaction forms, and short customized questionnaires to collect information from study subjects. REDCap provides: 1) a streamlined process for rapidly building a database; 2) an intuitive interface for collecting data, with data validation and audit trail; 3) automated export procedures for seamless data downloads to common statistical packages; 4) branching logic, file uploading, and calculated fields; and 5) a quick and easy protocol set-up. This system will be used by Duke for data management. All electronic linkages will fulfill regulations for protection of human subjects and requirements to minimize the risk of breach of confidentiality.

All study-related documents containing protected health information, e.g. enrollment logs, case report forms, diaries (Appendix E) completed by study participants, will be maintained in secure research offices at Duke, Boston University, and Cincinnati Children's Hospital, which are accessible to research staff only.

The study team will utilize a secure, encrypted, file transfer method for sharing study documents and data with the CDC. No personal identifiers will be included in any shared documents or datasets.

